Key secondary outcome measures include (1) weighing the sweat by gravimetric testing, (2) patient assessment of sweat production on a Hyperhidrosis Disease Severity Scale (HDSS) - also assessed at 1 month from baseline. All of the above will be tested for the contextual impact of type of intervention (Nd:YAG laser and IPL treatment, respectively), using a test for interaction. Safety around the use of Nd:YAG laser and IPL-treatment will be monitored by registering pain during treatment on a visual analogue scale, as well as monitoring adverse events immediately as well as one week after treatment. As for the purpose of further exploratory analyses (both benefits

and harms), all outcome measures will be re-collected 24 months after treatment.

Timelines and dissemination

For the collection of the primary data (i.e. primary endpoint being assessed after 1 month), First Patient First Visit (FPFV) will take place in January 2020 and Last Patient Last Visit (LPLV) will be in June 2020. We plan to present data internationally at e.g. the European Academy of Dermatology and Venerology as well as nationally to the Danish Dermatology Society and to the Hyperhidrosis Patient Association. Results will be published in an internationally recognised peer reviewed (biomedical) journal.

Trial registration: Danish Research Ethics Committee (approved, protocol number: SJ-689); ClinicalTrials.gov: NCT ??? pending.

INTRODUCTION

Background

Primary axillary hyperhidrosis is a condition with excessive secretion of sweat from the eccrine sweat glands of the armpits that affects between 1 and 5 % of the world's population². Numbers may be underestimated since this chronic disease debuts during adolescence and is unmentionable in many cultures and social environments. Hyperhidrosis may lead to malodour and cause large sweat patches on clothes, thus affecting dressing behaviour, social activities and job opportunities. As a direct consequence, many patients experience affected psychological and social behaviour, increased mental stress and low self-esteem³.

Several treatment modalities exist that may treat axillary hyperhidrosis. Systemic treatment with anticholinergic tablets is often reserved to hyperhidrosis that affects the entire body due to a substantial risk of adverse effects. Possible adverse effects (i.e. related to the intervention) include dry mouth and other mucous membranes, digestive problems, decreased ability to empty the bladder, visual disturbances and affected nervous system^{4,5}. Localised axillary hyperhidrosis is often treated by injections of botulinum toxin. Although this method is effective in many patients the procedure is painful, expensive and has to be repeated since the effect only last from four to nine months⁶. Recently, heating of the sweat glands with microwave technology has shown promising efficacy with minimal adverse effects. However, this treatment is very expensive and is only available at a few sites in Denmark. Surgery has also been performed, yet short-term and long-term efficiency is inferior to other methods⁶. Therefore, there is a need for efficient, safe, affordable and widely available alternatives to treat axillary hyperhidrosis.

An alternative method that have been proposed, could be heating and destroying sweat glands by Neodymium Yttrium Aluminium Garnet (Nd:YAG) laser or intensified pulsed light (IPL). These types of non-invasive light devices are widely available at dermatological clinics in Europe and is well-known to treat vascular lesions and undesired hair growth. The IPL has a 640 - 800 nm wavelength and the Nd:YAG laser a 1064 nm wavelength that penetrates deeply into the skin and target the melanin of the hair shaft. By adjusting the pulse length according to the theory of extended photo-thermolysis, light energy can be delivered through the hair shaft into surrounding sweat glands⁷. A previous pilot study has demonstrated significant and lasting reduction of axillary hyperhidrosis in six patients treated with Nd:YAG laser¹. Treatments were reported safe and efficient without any side effects. Likewise, two studies of a comparable but invasive Nd:YAG laser technique reported only temporary mild adverse effects and significant sweat reduction for up to 43 months after treatment^{8,9}. A single prospective study without a control group demonstrated increased sweat production following Nd:YAG laser treatment of

excessive hair growth¹⁰. Targeting hair and sweat glands is however not directly comparable due to different pulse lengths of the delivered energy.

Dynamic optic coherence tomography (d-OCT) is an imaging technique that utilizes infrared light to create two-dimensional horizontal or transverse images. Penetration depth is approximately 0.5 - 2 mm¹¹. The d-OCT technique allows *in situ* visualization of dynamic changes in blood flow and superficial skin structures in vital skin. Thus, the eccrine sweat glands and the surrounding blood supply can be followed over time without taking invasive tissue biopsies. Previous studies of histological changes after laser treatment of eccrine sweat glands have only been able to demonstrate limited structural changes and therefore, there is a need for improved imaging techniques to visualize laser-tissue-interactions.

Aim & Objectives

This study aims to assess the efficacy and safety of experimental intervention (either Nd:YAG laser *OR* IPL treatment) of an axilla with hyperhidrosis, relative to the contralateral untreated side, and to visualise laser-tissue interactions by Dynamic Optical Coherence Tomography.

Primary efficacy objective: to assess the effect of one of the experimental interventions (either Nd:YAG laser or IPL) treatment on eccrine sweat production by comparing treated and contralateral untreated axillae in patients eligible for botulinum-toxin therapy due to axillary hyperhidrosis. Sweat production is to be assessed at baseline and at one-month follow-up primarily by the iodine-starch test and secondly by gravimetric testing and questionnaires.

METHODS

Patient research partners (PRPs)

The study is designed without the assistance of PRPs. Collaboration between patients and professionals in developing and disseminating research projects is relatively new and the explorative nature and easily quantifiable outcomes chosen in this study reduces the need for the use of PRP. Should the study support the use of the new treatment, larger confirmatory studies will be needed and these will naturally include softer patient-rerouted outcomes and PRP collaboration.¹²

Trial design and allocation ratio

In a prospective within-person randomised trial, patients will be randomly allocated to receive laser treatment or IPL of one axilla while the other serve as a control (i.e. Right-Left and Left-Right, respectively). Primary endpoint will be assessed after 1 month. Treatments are performed

with a combined platform of non-ablative 640 - 800 nm IPL and 1064 nm long-pulsed Nd:YAG laser (Lumenis M22 system, Lumenis Ltd.) and laser energy is applied according to patient skin type.

Participants and settings

Eligibility criteria for participants & body sites

Legally competent women and men of at least 18 years, Fitzpatrick skin type I-III, suffering from severe axillary hyperhidrosis characterised by a value of 3 or 4 on the HDDS scale. Patients will not be considered eligible for inclusion if they take photosensitizing medication or have received other active treatments for axillary hyperhidrosis within the last five months. Axillary skin must be intact without wounds, scars or skin disease. Previous surgery, laser or microwave therapy in the axilla is not allowed. Patients who are pregnant or lactating at the time of enrolment will not be considered eligible either.

Settings and locations where the data will be collected

This project will take place from autumn 2019 to spring 2021 in an established research environment in the Dermatologic Department at Zealand University Hospital Roskilde. All patients will be included from January 2020 to June 2020 and will if possible be re-evaluated two years later.

Professor, doctor in medical science and Head of Department [name] is principal investigator. He is a highly qualified researcher with extensive counselling experience. Daily leader will be medical doctor, PhD [name] (EHT), who works as a clinician and a researcher. Medical doctor and PhD-students [name] and [name] will participate in daily study activities. The department accounts for all study facilities and technical equipment. The study has been approved by the Danish Research Ethics Committee (protocol number: SJ-689). Before enrolling the first patient, the trial was registered with clinicaltrials.gov (NCT Identifier: **Pending**).

Interventions

The intervention under investigation is one treatment with 640 - 800 nm IPL or non-ablative long-pulsed 1064 nm Nd:YAG laser (Lumenis M22 systems, Lumenis Ltd.). Laser or IPL energy will be applied according to patient skin type. Skin will be cooled during and after treatment to reduce inconvenience. On an optional basis, patients may also choose to receive topical anesthesia by lidocaine gel prior to treatment (EMLA 5%, Astra-Zenica, København S, Denmark). All patients will receive one treatment and will be followed up after one month. If possible,

patients will be contacted in order to perform a long-time follow up after 24 months. After completion of the project, patients are offered laser or IPL treatment of the axilla, which served as a control in the study.

Outcomes

The primary efficacy end point will be reduction in sweat production assessed as the change from baseline in an iodine-starch test at one month after treatment (i.e. 1 month after baseline).

Key secondary endpoints are (1) gravimetric testing of sweat production, and (2) patient-reported sweat production assessed on a 4-point Hyperhidrosis Disease Severity Scale (HDDS) for each axilla independently. The dynamic in situ laser-tissue interactions are monitored at baseline and at one-month follow-up. If possible, for further exploratory analyses, follow-up assessments will be repeated after 24 months.

Adverse events to treatment are monitored by the patient filling in a visual analogue scale of pain during treatment, by the laser surgeon reporting the presence of redness, oedema or ulceration immediately after treatment and by the patients filling in a questionnaire regarding adverse events one-week post-treatment.

Power and Sample size considerations

A sample size calculation was performed based on the assumptions that the main outcome measurement (the iodine-starch test for sweat) is continuous in nature, fairly normally distributed, and that an additional improvement in the intervention side of 30%points (assumed standard deviation=25%) will be considered clinically relevant. For a paired t-test of a normal mean difference with a two-sided significance level of 0.05 ($p < 0.05$), assuming a common standard deviation of 25% on the iodine-starch test with a correlation of 0.5, a sample size of 8 pairs is required to obtain a power of at least 80% to detect a mean difference between pairs of 30% (the actual power is 82.8%). It was decided to include and (within-person) randomise 10 patients for each intervention in order to consider a potential risk of drop-outs; a sample size of 10 pairs has a power of 92% to detect the mean difference between pairs of 30%.

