A detailed statistical analysis plan (SAP) will be developed during data collection while keeping the blind. In brief, the analyses will be based on mixed linear models, with a random effect for participant (1, 2, 3, ..., to 20) with a fixed effect for group (active or placebo), axilla (right or left), and the experimental intervention of secondary interest (Nd:YAG or IPL). For the primary analyses the type of experimental intervention (Nd:YAG or IPL) will be included as a main effect only; secondarily if the primary test hypothesis is rejected ($p < 0.05$; $H_0: \mu_{\text{Active}} = \mu_{\text{Placebo}}$) we will

add a test for interaction to compare the net benefit for Nd:YAG vs. Placebo and IPL vs. placebo.

RESULTS COLLECTED (FOR REPORTING)

Table 1 Characteristics of participants AND primary & key secondary end points.			
	Baseline	Follow-up (1 week from baseline)	Follow-Up (1 month from baseline)
Age (years)	X	-	-
Sex: Female, no. (%)	X	-	-
Skin type	X	-	-
Family medical history	X	-	-
Personal medical history	X	-	-
Medication	X	-	-
Age of onset of hyperhidrosis	X	-	-
Previous history of hyperhidrosis	X	-	-
Primary Outcome Measure:			
Iodine-starch test incl. Photos (%)	X	-	X
Key Secondary Outcome Measures:			
Dynamic OCT imaging (photos)	X	-	X
Gravimetric testing (mg/5 min)	X	-	X
HDSS score for each axilla individually (4-point rang scale)	X	-	X
Binary questions for patient:			
1) Effect from treatment? no. (%)	-	-	X
2) Adverse effects from treatment? no. (%)	-	-	X
3) Registration of whether the patient wish to receive laser treatment on control axilla after the study? no. (%)	-	-	X
Monitoring of adverse events			
Patient: VAS of pain during treatment (0-100 mm)	X	-	-
Physician: Report of redness, oedema and ulceration immediately after treatment (0-100 mm)	X	-	-
Patient: questionnaire of adverse effects (one-week post treatment)	-	X	-

OTHER**Perspectives and dissemination**

Given a successful outcome of an investigation of long-pulsed Nd:Yag laser or IPL treatment for axillary hyperhidrosis, the laser treatment could potentially be implemented in the everyday practice, since Nd:YAG lasers and IPL devices are already widespread in European dermatological hospital departments and clinics.

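### Safety is to be judged against the untreated axilla, but no harm item is specified for each axilla, so the plan as written cannot deliver that comparison

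*Combined protocol and SAP*

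**What the plan says.** One sentence under Aim & Objectives sets the aim. It opens "This study aims to assess the efficacy and safety of experimental intervention" and, after naming the two devices, continues "of an axilla with hyperhidrosis, relative to the contralateral untreated side". Read plainly, the untreated axilla is the comparator for safety as well as for efficacy.

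Harm monitoring is described under Outcomes in three parts:

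- Pain, scored by the patient: "Adverse events to treatment are monitored by the patient filling in a visual analogue scale of pain during treatment".
- Skin signs, noted once the session ends: the laser surgeon states whether any redness, oedema or ulceration is seen.
- Later effects, taken from a patient form: "by the patients filling in a questionnaire regarding adverse events one-week post-treatment".

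Table 1 repeats these and adds a yes/no question at one month on whether treatment caused adverse effects. It lists the questionnaire as "Patient: questionnaire of adverse effects (one-week post treatment", with no side named. For the severity scale, by contrast, it has "HDSS score for each axilla individually (4-point rang scale".

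The Statistical methods section outlines mixed linear models for the analyses in general. It names no comparison of harms between axillae and leaves detail to a SAP to be written during data collection. The Blinding (masking) section accepts that patients, physicians and outcome assessors may know the allocation.

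**The concern.** A within-person design supplies a matched control for local skin reactions at no extra cost: the other axilla of the same patient on the same day. That control is useful only if reactions are recorded on both sides in the same way. Here the specified items ask what the treatment did. A record of that kind gives a proportion of patients with reported treatment effects and nothing to subtract from it.

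Without the control side, the reporter must decide what was due to treatment. Background irritation in the treated axilla, whatever its source, may be put down to the laser or IPL. A real reaction may equally be explained away. The patient making that judgement knows which side was treated. The stake is whether the trial can answer the safety question in its own aim.

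**Working it through.** **The plan's own figures.** The only sample-size calculation concerns the primary efficacy outcome. The inputs, from Power and Sample size considerations, are SD 25, correlation 0.5, difference 30 and two-sided alpha 0.05.

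- SD of the paired difference = 25 × √(2 × (1 − 0.5)) = 25.
- Exact power of the paired t-test (noncentral t): 82.8% with 8 pairs and 92.0% with 10 pairs.

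Both agree with the stated 82.8% and 92%. They have no bearing on harms, for which the plan gives no figure.

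**The harm items against the aim.**

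| Item | Reported by | Side specified? | Consequence |
|---|---|---|---|
| Pain during treatment (VAS) | Patient | No | No natural control-side counterpart, so little is lost |
| Redness, oedema, ulceration straight after treatment | Laser surgeon | No | Timing ties it largely to treatment; a control-side record is possible but not specified |
| Questionnaire at one week | Patient | No | Depends on the patient's view of cause, days later, knowing the treated side |
| Yes/no adverse-effect question at one month | Patient | No | The question itself asks for attribution to treatment |
| HDSS (not a harm item, for contrast) | Patient | Yes, each axilla | Can be compared between sides |

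The last row shows that the plan specifies sides for a patient-reported item where it intends to compare them. No harm item has that specification, and no section describes a treated-versus-untreated table of harms.

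**Size.** There are 10 patients per device and 20 in all. One misattributed event changes a device's rate by 1/10 = 10 percentage points and the pooled rate by 1/20 = 5 points. This needs no assumption about how often misattribution occurs.

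**What per-axilla recording would and would not give.**

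- If no patient reacts on the treated side only, the exact two-sided 95% upper limit for that proportion is 1 − 0.025^(1/10) = 30.8% for one device and 1 − 0.025^(1/20) = 16.8% pooled.
- An exact two-sided McNemar test needs at least 6 discordant pairs, all in one direction: 2 × 0.5^6 = 0.031, whereas 5 pairs give 2 × 0.5^5 = 0.0625.
- With 20 pairs, no control-only events and assumed treated-only rates of 20%, 30% and 40%, power is about 20%, 58% and 87%. These rates are assumptions; the documents give none.

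The paired table should therefore be descriptive, with intervals, and not a test.

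**The case against.** Outside the aim sentence, safety is described as monitoring, and only the primary efficacy objective spells out a comparison of treated with untreated axillae. The detailed analysis is left to a later SAP. On this view the mismatch is one loosely worded sentence. That has force, and rewording the sentence would be a valid remedy. But a SAP written during data collection cannot supply control-side observations that the forms did not ask for.

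Three stronger readings are tempting, and the documents do not support them.

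- A reader might infer that harms are definitely not recorded by side. The questionnaire and the physician's form are not shown and may ask for location. The supportable statement is that side is not specified. Table 1 names no side for the iodine-starch and gravimetric tests either, although the primary objective makes clear that those compare axillae.
- A reader might infer that every efficacy measure is taken on both sides and only harms are not. That is too broad: the one-month yes/no question on whether treatment had an effect also names no side.
- A reader might infer that irritation from the sweat tests, used on both axillae, inflates the harm rate by some calculable multiple. The documents do not say that the tests irritate skin, give no rate, and do not state the order or interval between baseline tests and treatment. A shared Baseline column in Table 1 is a visit label and does not establish sequence. Test irritation is only one possible background source, and no multiple can be derived. A patient with the same irritation on both sides might also not blame the treatment at all.

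It is also fair to object that cooling and the optional anaesthetic go with the treated side. A paired contrast would then estimate the effect of the whole package and not of the light alone, and patients would still know the treated side. This limits the interpretation, but the comparison would still be controlled, which the present plan does not provide.

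**Conclusion.** The concern holds as a gap between a stated aim and the data specified to meet it. The aim makes the untreated axilla the comparator for safety; no harm item is specified for that axilla, so the within-person safety comparison cannot be made as the plan is written. The weakness lies mainly in the one-week questionnaire and the one-month question. The immediate skin report is less exposed because of its timing, and pain during treatment is outside the point.

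The only size that can be given without outside figures is 10 percentage points in a device's rate per misattributed event. Neither the number nor the direction of such events can be estimated from the documents. The conclusion assumes that the forms follow the text and carry no side field; if they already do, only the protocol wording and the planned table need attention. The primary efficacy analysis and its sample size are not affected.

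**What to change.** 1. Ask the one-week and one-month adverse-effect items separately for right and left axilla, as findings present or absent, without asking the patient to say what caused them.
2. Have the physician record redness, oedema and ulceration on both axillae at the same time after treatment. Outcomes speaks of presence while Table 1 attaches a 0-100 mm scale; state which applies, and keep a present/absent field so that counts can be made.
3. State in the protocol when the baseline sweat tests are done relative to treatment, so that background reactions can be interpreted.
4. In the SAP, plan one descriptive table, pooled and per device, counting patients with a reaction on the treated side only, the untreated side only, both and neither. Give exact 95% intervals for the two one-sided proportions. Note that the contrast covers the whole package (light, cooling, optional anaesthetic) and that the intervals will be wide.
5. Make Aim & Objectives, Outcomes and Table 1 agree with this.

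If per-axilla recording is not adopted, reword the aim so that only efficacy is relative to the untreated side and safety is descriptive for the treated side.

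The cost is slightly longer forms, a brief look at the second axilla and one extra table. No new visit or procedure is needed.

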A detailed statistical analysis plan (SAP) will be developed during data collection while keeping the blind. In brief, the analyses will be based on mixed linear models, with a random effect for participant (1, 2, 3, ..., to 20) with a fixed effect for group (active or placebo), axilla (right or left), and the experimental intervention of secondary interest (Nd:YAG or IPL). For the primary analyses the type of experimental intervention (Nd:YAG or IPL) will be included as a main effect only; secondarily if the primary test hypothesis is rejected ($p < 0.05$; $H_0: \mu_{\text{Active}} = \mu_{\text{Placebo}}$) we will

add a test for interaction to compare the net benefit for Nd:YAG vs. Placebo and IPL vs. placebo.

RESULTS COLLECTED (FOR REPORTING)

Table 1 Characteristics of participants AND primary & key secondary end points.			
	Baseline	Follow-up (1 week from baseline)	Follow-Up (1 month from baseline)
Age (years)	X	-	-
Sex: Female, no. (%)	X	-	-
Skin type	X	-	-
Family medical history	X	-	-
Personal medical history	X	-	-
Medication	X	-	-
Age of onset of hyperhidrosis	X	-	-
Previous history of hyperhidrosis	X	-	-
Primary Outcome Measure:			
Iodine-starch test incl. Photos (%)	X	-	X
Key Secondary Outcome Measures:			
Dynamic OCT imaging (photos)	X	-	X
Gravimetric testing (mg/5 min)	X	-	X
HDSS score for each axilla individually (4-point rang scale)	X	-	X
Binary questions for patient:			
1) Effect from treatment? no. (%)	-	-	X
2) Adverse effects from treatment? no. (%)	-	-	X
3) Registration of whether the patient wish to receive laser treatment on control axilla after the study? no. (%)	-	-	X
Monitoring of adverse events			
Patient: VAS of pain during treatment (0-100 mm)	X	-	-
Physician: Report of redness, oedema and ulceration immediately after treatment (0-100 mm)	X	-	-
Patient: questionnaire of adverse effects (one-week post treatment)	-	X	-

OTHER**Perspectives and dissemination**

Given a successful outcome of an investigation of long-pulsed Nd:Yag laser or IPL treatment for axillary hyperhidrosis, the laser treatment could potentially be implemented in the everyday practice, since Nd:YAG lasers and IPL devices are already widespread in European dermatological hospital departments and clinics.

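### No clinician looks at the skin for harm after the treatment day: at one month the only designated harm item is a patient yes/no, so persistent skin changes may go unverified or uncharacterised

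*Combined protocol and SAP*

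**What the plan says.** The Aim & Objectives section puts safety beside efficacy: "This study aims to assess the efficacy and safety of experimental intervention".

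The Outcomes section collects harms in three ways: a pain scale during treatment, a physician's report ("by the laser surgeon reporting the presence of redness, oedema or ulceration immediately after treatment"), and a patient report ("by the patients filling in a questionnaire regarding adverse events one-week post-treatment"). The Summary gives the same window: "monitoring adverse events immediately as well as one week after treatment".

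Table 1 agrees on the timing. The row "Physician: Report of redness, oedema and ulceration immediately after treatment (0-100 mm" has an X at baseline and dashes at one week and one month. The row "Patient: questionnaire of adverse effects (one-week post treatment" has an X at one week only. The one-month column contains a single harm item, "2) Adverse effects from treatment? no" (to be reported as number and percentage). It stands under "Binary questions for patient", outside the table's adverse event block.

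The patient attends at one month for the iodine-starch test with photographs, gravimetry and dynamic OCT (d-OCT). The Summary adds that all outcome measures, for benefits and harms, will be collected again at 24 months for exploratory analysis. The sections on settings, interventions and outcomes make that follow-up depend on whether it is possible, and Table 1 has no column for it.

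**The concern.** The plan itself treats redness, oedema and ulceration as findings for a physician to judge. A look at the skin just after treatment can show that a reaction occurred. It cannot show whether the reaction cleared or left a scar or a change in pigment; that needs a second look.

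The design is well suited to one. The eligibility criteria require axillary skin free of wounds, scars and skin disease, and each patient has an untreated axilla for comparison. At one month both axillae are already being tested.

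At stake is the safety half of the aim. Without a later clinician record, the report can give immediate reactions and patient replies, but not a verified account of what persisted. Participants are offered treatment of the control axilla after the study, and the section on perspectives mentions possible everyday use. Both would draw on the safety result.

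**Working it through.** The documents give no figure for harms, so there is none to reproduce. The sample size figures concern the iodine-starch test only and do not bear on this point. The check is a reading of the schedule, from the Summary, Interventions, Outcomes and Table 1.

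| Time | Clinician skin report | Patient harm item | Other record of the skin |
|---|---|---|---|
| Baseline and treatment | Redness, oedema, ulceration | Pain scale | Photographs, d-OCT |
| 1 week | None | Adverse effect questionnaire | None |
| 1 month | None | One yes/no | Photographs, d-OCT; no safety reading planned |
| 24 months | Not specified | Conditional, exploratory | Conditional, exploratory |

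**Step 1: count the clinician records.** There are 10 + 10 = 20 patients with one treated axilla each, so 20 treated and 20 control axillae. With full attendance, the plan produces a clinician harm record for 20 treated axillae on day 0, for 0 of 20 at one week, and for 0 of 20 at one month (0 of 40 axillae counting the control side).

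**Step 2: what the one-month yes/no can answer.** A yes does not give type, severity, duration or resolution. Discomfort that has passed and a lasting scar are recorded alike. Unlike the HDSS, the item is not marked as scored for each axilla. A no rests on what the patient has noticed.

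**Step 3: what the one-month images can answer.** The photographs belong to the sweat test, the primary efficacy measure. d-OCT is there to follow laser-tissue interaction and is listed among the key secondary outcomes. Either might show an injury, but no reader, list of findings or reporting rule for safety is given. Nor do the documents say whether the photographs show bare skin well enough for that use.

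**Step 4: what the 24-month follow-up can answer.** Enrolment from January to June 2020 plus 24 months gives January to June 2022, which is after the project period stated under settings (to spring 2021). The physician item is defined by its timing just after treatment, so it is unclear what repeating it would mean. A change present at one month that later faded could not be recovered. If a patient has by then accepted treatment of the control axilla, the untreated reference is lost as well.

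**Result.** Between the one-week questionnaire and the conditional 24-month follow-up there is one designated harm item, a patient yes/no, and no clinician assessment.

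**The case against.** The strongest reply is that harm is covered after the first week. The patient is asked at one month, images of the skin are made at that visit, and a 24-month re-collection of harms is planned. All of this is true. A reader might infer that nothing except the yes/no covers harm after one week, and the documents do not support that. What is missing is narrower: a clinician assessment, or a designated safety reading, at one month.

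A second reply is that an ulcer appearing in the days after treatment falls before the one-week questionnaire, and one still present later meets the one-month question. To be lost altogether it would have to escape both patient reports. This also stands. A reader might infer that delayed ulcers will be missed, but the documents do not say how often ulceration appears late after these devices. That it can do so is an assumption, and the point does not need it. The gap lies mainly in verifying and describing what persists.

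Third, a zero in the physician row would carry its own label as an immediate finding, and no passage plans to present it as an overall ulceration rate. This is fair.

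Fourth, the study calls itself explorative and expects larger confirmatory studies. That lowers the urgency, but safety remains a stated aim. The detailed SAP still to be written cannot help either, because it cannot analyse an examination that was never made.

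**Conclusion.** The point holds as a modest gap in outcome assessment. The clinician skin report is confined to the treatment day. The one-month visit adds only an unspecific patient yes/no, so unresolved redness or ulceration, scarring or pigment change may go unverified or uncharacterised in patients who are present in the clinic. The size is 0 of 20 treated axillae with a planned clinician harm record after day 0. How many changes would go undescribed cannot be estimated, because the documents give no injury rates.

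The small sample should not be used as evidence here. With no events, the exact two-sided 95% upper limit is 1 − 0.025^(1/10) = 30.8% for 10 patients and 1 − 0.025^(1/20) = 16.8% for 20. A reader might infer that these limits show the cost of the timing. They follow from the sample size and would be the same with a one-month examination.

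The conclusion assumes that a dash in Table 1 means no collection, which the Outcomes text supports, and that the yes/no has no structured follow-up questions, since none are described. The efficacy analysis is not affected.

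**What to change.** In Table 1, add an X for the physician skin report in the one-month column, recorded for each axilla with the control side as reference. It should cover redness, oedema, ulceration, scar and pigment change. At minimum, designate a safety reading of the existing one-month photographs against the same list; this is weaker, because the photographs were planned for the sweat test.

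Align the harm-timing text in the Summary and in Outcomes, so that both name the treatment day, one week and one month. Report one-month findings separately from immediate ones. Since the item will be used twice, also reconcile its form: Outcomes records presence, while Table 1 gives it a 0-100 mm scale.

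The cost is a few minutes at a visit that already takes place and one case report form page. No extra visit, staff, invasive procedure or change in sample size is needed.
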